3.2. General Methods

In general, tables will summarize data by transfusion history stratum at Day 1. All statistical analyses will be performed using SAS statistical software Version 9.4 or higher, unless otherwise noted. For categorical variables, descriptive statistics will include frequency count and percentage. If missing is observed, a “Missing” category will be added without percentage. For shift tables, total rows and columns will not include patients from the “Missing” category except the “Missing” column and row and percentage will be calculated based on evaluable patients. For continuous variables, descriptive statistics are number of patients, mean, median, standard deviation (SD), 25th percentile (Q1), 75th percentile (Q3), minimum, and maximum.

For parameters assessed across multiple visits, by-visit summaries will be presented for planned visits from Table 1 and Table 2.

Minimum and maximum values will be presented to the same decimal precision as the raw values, mean, median, Q1, and Q3 values to one more decimal than the raw values, and the SD to two more decimals than the raw values. All percentages will be presented to one decimal place. All p-values will be presented with 4 decimal places and will be shown as ‘<0.0001’ if the value is smaller than 0.0001.

Relative study day will be provided in data listings. Day 1 is defined as the date of first treatment. Other study days are defined relative to Study Day 1. Relative day is calculated as (date of interest - date of the first treatment + 1) for study days on or after the date of the treatment start, and as (date of interest - date of the first treatment) for study days prior to the date of the treatment start.

Figures will be created to plot the data where it is deemed necessary. All data collected on study in the eCRF will be included in data listings.

3.3. Baseline Definitions

Baseline values for Hb will be defined as the mean of the screening and Day 1 pre-treatment values. If one of the two assessments is missing, then a single assessment prior to the start of study treatment will be defined as baseline.

History of RBC transfusions will be gathered for each patient for up to 16 weeks before start of study treatment. Baseline RBC transfusion burden units per 8 weeks will be defined as the summed units transfused in the 8 weeks up to pre-dose Day 1 (Rel Day -55 to 1).

For all other analyses, baseline will be defined as the most recent non-missing measurement prior to the first administration of study drug.

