5.1 Inclusion Criteria

Participants are eligible to be included in the study only if all the following criteria apply:

Informed Consent

1. Patient has provided documented informed consent; the informed consent form (ICF) must be reviewed and signed by each patient prior to any study-related assessments/procedures being conducted.

Age

2. Age \geq 18 years at time of first dose

Sex and Contraceptive/Barrier Requirements

3. Patients, if female and of childbearing potential, must agree to use acceptable methods of contraception and agree not to donate ova from study start to 90 days after the last dose of study drug, and who if male are willing to use acceptable methods of contraception and agree not to donate sperm, from study start to 90 days after the last dose of study drug.

Disease Specific Requirements

- 4. Documented diagnosis of idiopathic/de novo MDS according to 2016 WHO classification (see Appendix C) that meets IPSS-R classification (see Appendix B) of very low, low, or intermediate risk disease, and:
 - < 5% blasts and no Auer rods in bone marrow based on local pathology review
 - < Intermediate risk cytogenetic abnormalities per IPSS-R
- 5. Anemia defined as:
 - NTD: Subjects with mean Hb concentration < 10.0 g/dL on 2 measurements (1 performed within 3 days prior to W1D1 and the other performed 7 to 28 days prior to W1D1, not influenced by RBC transfusion within 7 days of measurement) and < 3 RBC transfusions for anemia in the prior 16 weeks before W1D1 of etavopivat dosing

OR

- Transfusion Dependent: Subjects having received ≥ 3 units of RBCs for the treatment of anemia within 16 weeks prior to W1D1
- 6. Serum erythropoietin level > 200 U/L, OR, if \leq 200 U/L, subject is non-responsive, refractory, or intolerant to erythropoiesis-stimulating agents, or erythropoiesis-stimulating agents are contraindicated or unavailable.
- 7. Eastern Cooperative Oncology Group performance status of ≤ 2 (see Appendix D)

- 8. Subject is non-responsive, refractory, or intolerant to luspatercept, or luspatercept is contraindicated or not indicated.
- 9. No alternative treatment options are available and/or appropriate for the subject, at the discretion of the investigator.
- 10. Patient is willing and able to adhere to the study visit schedule and other protocol requirements

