1.2. Study Design

1.2.1. Synopsis of Study Design

4202-ONC-203 is a multicenter, open-label Phase 2 study in adult patients with very low, low risk, or intermediate risk MDS per the Revised International Prognostic Scoring System (IPSS-R) classification. The study will enroll approximately 45 patients.

Initially, 6 patients will be enrolled and dosed a minimum of 4-weeks with etavopivat 400 mg daily to confirm if safety, exposure, and pharmacological response (PK/PD profile) are consistent with prior experience of etavopivat dosing in healthy volunteers and patients with SCD or thalassemia.

Approximately 45 MDS patients (inclusive of the initial 6 patients enrolled for safety/PK/PD confirmation) will be enrolled and evaluated for an erythroid response based on the revised MDS IWG 2018 criteria (see protocol Appendix A). Response assessment will be based on the individual patient's transfusion history in the 16 weeks prior to enrollment:

- NTD patients (received \leq 2 RBC units for anemia within the prior 16 weeks):
Hb increase of \geq 1.5 g/dL over a continuous 8-week treatment period and no transfusion of RBC units for anemia over a continuous 8-week treatment period
 - Approximately 15 NTD patients may be enrolled in this study
- LTB patients (received 3 to 7 RBC units within the prior 16 weeks): No transfusion of RBC units for anemia over a continuous 8-week treatment period
 - Approximately 15 LTB patients may be enrolled in this study
- HTB patients (received \geq 8 RBC units in the prior 16 weeks): \geq 50% reduction in RBC units transfused over a continuous 8-week period.
 - Approximately 15 HTB patients may be enrolled in this study

A futility assessment will be triggered when 15 patients across all strata or 8 patients in a single stratum reach 24 weeks of treatment, whichever occurs first. If both criteria are met at the same time, the overall futility assessment will be performed.

The futility criterion is defined as follows:

- All strata (n=15): \leq 3 responses meeting HI-E criteria, sustained from Week 16 to Week 24.
- Single stratum (n=8): 0 (zero) responses.

If either the overall or single stratum futility criterion is met, enrollment may discontinue for futility or further enrollment restricted to specific subsets of patients based on prior transfusion history may be considered. If neither criterion is met, enrollment will continue until a total of 45 response-evaluable patients are available at Week 24.

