4.2.2. Analysis of Secondary Endpoints

4.2.2.1. Transfusion Burden

For the LTB and HTB strata only, the total RBC units transfused and % reduction from baseline will be summarized for each of the following 8-week study intervals: Week 1 to 8 (Rel Day 2 to 57), Week 9 to 16 (Rel Day 58 to 113), Week 17 to 24 (Rel Day 114 to 169), Week 25 to 32 (Rel Day 170 to 225), Week 33 to 40 (Rel Day 226 to 281), Week 41 to 48 (Rel Day 282 to 337).

% reduction from baseline in RBC transfusion burden is defined as

$$-100 \times \frac{\text{Total RBC Units Transfused During Interval}}{\text{Baseline RBC Units Transfused Per 8 Weeks}}$$

Patients who have discontinued treatment prior to completing the specified interval will be excluded from the analysis.

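### Baseline transfusion burden uses 8 weeks although strata use 16, so percent reduction can be undefined for an LTB patient and rests on a noisier reference for HTB patients

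*SAP*

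**What the plan says.** **Classification uses 16 weeks.** SAP Section 1.2.1 defines LTB as 3 to 7 RBC units, and HTB as 8 or more, counted over the 16 weeks before enrollment ("within the prior 16 weeks" for LTB). Protocol Section 5.1 defines transfusion-dependent eligibility as "Subjects having received ≥ 3 units of RBCs for the treatment of anemia within 16 weeks prior to W1D1". Neither asks for any unit in the last 8 weeks. Protocol Appendix A compares on-treatment transfusion with the 16 weeks before treatment in both strata.

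**The baseline uses 8 weeks.** SAP Section 3.3 collects up to 16 weeks of history but defines baseline burden as "the summed units transfused in the 8 weeks up to pre-dose Day 1", that is, relative days -55 to 1.

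**Where the baseline is used.** SAP Section 4.2.2.1 states: "For the LTB and HTB strata only, the total RBC units transfused and % reduction from baseline will be summarized". Its denominator is "Baseline RBC Units Transfused Per 8 Weeks". SAP Section 4.2.1.1 divides by the same quantity to decide whether an HTB patient had the 50% reduction needed for the primary response.

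**Rules for special cases.** The only exclusion in Section 4.2.2.1 is: "Patients who have discontinued treatment prior to completing the specified interval will be excluded from the analysis". Section 3.9 makes no substitutions unless otherwise specified. It treats a transfusion with no year or no date as falling before the 8-week window. SAP Section 5 does not list the 8-week baseline among the changes from protocol.

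**The concern.** A patient can be eligible and LTB on 16 weeks of history yet have nothing in the window that supplies the denominator. Percent reduction then cannot be computed for that patient, however the patient fares on treatment. Whether this happens depends on when the transfusions fell, not on disease burden or response. The undated-transfusion rule pushes the same way, since it can only lower the baseline.

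For HTB patients a zero is less likely, but the denominator matters more because it feeds the primary response. Using half of the collected history makes each patient's reference level less stable, and a chance low or high 8 weeks can move a patient across the 50% line.

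The abbreviated SAP has dropped most other secondary efficacy endpoints, so percent reduction is a main output of the one secondary efficacy analysis it still describes.

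**Working it through.** The plan states no figure to reproduce here. The check is of logic, followed by an illustration of size.

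**1. Window length.** SAP Section 3.2 has no Day 0, so days -55 to -1 plus Day 1 give 55 + 1 = 56 days, or 8 weeks. The earlier 8 weeks of the 16-week history do not enter the baseline.

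**2. Zero denominator.** Take an LTB patient with k units (k = 3 to 7), all before day -55. The baseline is 0. Percent reduction has the form (quantity) / 0 for 0, 2, 4 or any other number of on-treatment units, so it is undefined in every interval. (The formula printed in Section 4.2.2.1 also omits the subtraction of baseline that Section 4.2.1.1 has. That is a separate matter; the denominator is zero either way.)

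**3. How often.** The documents give no transfusion timing, so this is a range under two assumed models.

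- *Independent sessions, evenly spread over 16 weeks.* P(zero baseline) = 0.5^s for s sessions: s = 2 gives 25%, s = 3 gives 12.5%, s = 4 gives 6.3%.
- *Strictly regular spacing of T weeks, two or more sessions.* Two sessions inside the earlier 8 weeks need T below 8. No session in the later 8 weeks needs T of at least 8. Both cannot hold, so P = 0%.

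The range is therefore 0% to 25% for two sessions and 0% to 12.5% for three.

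**4. Scale against the planned 15 LTB patients.** This adds the assumption that totals of 3 to 7 units are equally likely.

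| Timing model | Average P(zero) | Expected of 15 | P(at least one) |
|---|---|---|---|
| Regular spacing, two or more sessions | 0% | 0 | 0% |
| Single units, independent | (12.5 + 6.25 + 3.125 + 1.5625 + 0.78125)/5 = 4.8% | 0.7 | 53% |
| Two-unit sessions, independent | (25 + 25 + 12.5 + 12.5 + 6.25)/5 = 16.3% | 2.4 | 93% |

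The last column is 1 - (1 - P)^15.

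**5. Noise.** Let the two 8-week counts have equal variance v and be independent. Then Var[(X1 + X2)/2] = (v + v)/4 = v/2, half the variance of the 8-week count alone.

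**6. Effect on an HTB patient.** Take 8 units in 16 weeks and 2 units in an on-treatment interval. If 3 of the 8 fell in the last 8 weeks, the 8-week baseline gives (3 - 2)/3 = 33.3%, not a response in that interval. The 16-week baseline is 8/2 = 4 and gives (4 - 2)/4 = 50%, a response. If instead 6 fell in the last 8 weeks and 3 units were given on treatment, the 8-week baseline gives (6 - 3)/6 = 50% and the 16-week baseline (4 - 3)/4 = 25%. Status can change in either direction.

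**7. Zero baseline in HTB.** With 8 units, independent timing gives 0.5^8 = 0.4% as single units or 0.5^4 = 6.3% as two-unit sessions; regular spacing gives 0%.

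**8. With the 16-week total divided by 2.** LTB baseline runs from 3/2 = 1.5 to 7/2 = 3.5, and HTB baseline is at least 8/2 = 4. Neither can be zero.

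**The case against.** **Little is lost for LTB patients.** A reader might infer that a zero-baseline patient leaves the secondary endpoint, or that the LTB primary result is affected. The documents do not support either. Section 4.2.2.1 also summarizes total units, which needs no denominator. The transfusion-independence part of the endpoint needs none, and LTB primary response is simply 8 transfusion-free weeks. Only the percent-reduction value is lost, in a descriptive summary where the reported number of patients would show the gap. This stands.

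**The frequency may be zero.** Protocol Section 8.2.2.1 and Appendix G treat transfusion as planned at an interval, and strict regularity rules out a zero baseline. The study was also terminated early and efficacy is limited to patients who completed Week 24, so 15 LTB patients is only a planned number. This stands too, and is why the size is given as a range starting at 0%.

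**An 8-week baseline is like-for-like with 8-week intervals.** The Protocol's endpoint wording in Sections 3.1 and 9.6.1 fixes no reference window for the 50% reduction, so the 8-week choice does not contradict those sections. But a 16-week total divided by 2 is also a rate per 8 weeks, and it follows Appendix A and the strata.

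**A narrower repair exists.** A zero-baseline rule in Section 4.2.2.1 would leave the primary endpoint alone. That would close the LTB gap, but not the noise or the possible zero in the HTB primary rule. The objection is right that changing the baseline touches the HTB primary response and the Section 3.9 date rule, so it is more than a one-line edit.

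**Conclusion.** The concern holds within limits. The gap itself is certain from the text: an eligible LTB patient can have a zero denominator, and no rule says what to do. How often that happens cannot be known from the documents. It is 0% to 25% with two sessions and 0% to 12.5% with three, and the upper ends rest on independent, evenly spread timing. For LTB the damage is confined to percent reduction.

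For HTB the same baseline enters the primary response. It has twice the variance of the 16-week average if the two 8-week counts are independent with equal variance, and a zero is possible though less likely. It would be going too far to say that the primary result is biased in a known direction, since the examples show status moving both ways. The change is worth making; the point does not invalidate the planned analysis.

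**What to change.** - In SAP Section 3.3, define baseline burden per 8 weeks as the total RBC units in the 16 weeks before Day 1 divided by 2.
- In SAP Section 3.9, replace the rule that places undated transfusions more than 8 weeks before entry with one that fits the 16-week window. For example, count an undated transfusion in the baseline if it was counted when the stratum was assigned.
- Record the change in SAP Section 5, because HTB primary responder status may change.
- Report HTB primary response on the 8-week baseline as a sensitivity analysis, and state how many LTB and HTB patients have an 8-week baseline of zero.

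**Cost.** No new data are needed, since the 16-week history is already collected. The price is a small amount of extra programming and output, and the possible reclassification of some HTB responders. As the SAP was written after early termination of an open-label study, both versions of the HTB result should be shown openly.

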3.4. Methods of Pooling Data

No data pooling will be performed in this study.

3.5. Adjustments for Covariates

No statistical modeling will be applied in this study, therefore adjustment for covariates would not be applicable.

3.6. Multiplicity

There are no planned multiplicity corrections for this study.

3.7. Subgroup Analysis

No analyses of patient subgroups are planned. However, summary tables will include separate displays for each transfusion history stratum.

3.8. Withdrawals and Dropouts

Patients who are withdrawn or discontinue from the study may be replaced to achieve the threshold of 45 evaluable patients at Week 24. If enrollment is discontinued in one or more transfusion history groups after the interim assessment, enrollment in the remaining transfusion history group(s) may be increased to allow for 45 total evaluable patients at study completion.

3.9. Missing Data

Unless otherwise specified, there will be no substitutions made to accommodate missing data. All data recorded on the case report form (CRF) will be included in data listings that will accompany the CSR.

RBC transfusion history dates may be imputed for the purposes of calculating baseline RBC transfusions. If the day or month are missing, the first day of the month or month of the year will be assumed. If the year is missing or the full date is missing, the RBC transfusion will be assumed to have occurred more than 8 weeks prior to study entry (to be excluded from the baseline calculation).

When tabulating adverse event data, partial dates will be handled as follows. If the day of the month is missing, the onset day will be set to the first day of the month unless it is the same month and year as the first dose. In this case, in order to conservatively report the event as treatment-emergent, the onset date will be assumed to be the date of treatment initiation. If the onset day and month are both missing, the day and month will be assumed to be January 1, unless the event occurred in the same year as the study treatment. In this case, the event onset will be coded to the date of first dose in order to conservatively report the event as treatment-emergent. A completely missing AE onset date will be coded as the day of first treatment

unless the end date is prior to study start. In this case, no imputation will be done and the AE will be considered as not treatment-emergent.

Partial start dates for concomitant medications will be handled in the same manner as partial adverse event onset dates. For concomitant medication end dates, where the day of the month is missing, it will be imputed to the last day of the month. If both day and month are missing, the day and month will be assumed to be December 31st.

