 - Patients with incidental histologic findings of prostate cancer (T1a or T1b) are eligible
- 16. History of unstable or deteriorating cardiac or pulmonary disease within 180 days prior to consent including but not limited to the following:
 - Unstable angina pectoris or myocardial infarction or elective coronary intervention
 - Heart disease, heart failure as classified by the New York Heart Association classification 3 or higher, or significant arrhythmia requiring treatment,
 - Pulmonary fibrosis or pulmonary hypertension which are clinically significant ie, ≥ Grade 3 National Cancer Institute (NCI) Common Terminology Criteria for Adverse Events (CTCAE) version 5.0 (or higher)
- 17. Uncontrolled hypertension, defined as repeated elevation of diastolic blood pressure ≥ 100 mmHg despite adequate treatment
- 18. Any condition affecting drug absorption, such as major surgery involving the stomach or small intestine (prior cholecystectomy is acceptable).

Prior/Concomitant Therapy

- 19. Prior treatment with azacitidine (injectable or oral) or decitabine (injectable or oral)
- 20. Use of erythropoietin (ESA), other hematopoietic growth factor treatment or lenalidomide within 30 days of starting study treatment or anticipated need for such agents during the study. If patient has stage 3 or 4 chronic kidney disease (CKD) defined by 30 mL/min/1.73 m² ≤ eGFR <60 mL/min/1.73 m² and has been on a stable ESA dose for ≥6 months and plans to continue on ESA at the same dose throughout the duration of the study, patient is eligible.
- 21. Prior use of luspatercept:
 - NTD patients must not have received luspatercept within 30 days prior to W1D1 treatment
 - Transfusion-dependent (TD) patients must not have received luspatercept within 80 days prior to W1D1 treatment
- 22. Receiving or use of concomitant medications that are strong inducers of cytochrome P450 (CYP)3A4/5 (see Appendix F) within 14 days of starting study treatment or anticipated need for such agents during the study.
- 23. Prior allogeneic or autologous stem cell transplant or any organ transplant
- 24. Initiation of a new chelation therapy within 90 days before the first dose of study treatment

Prior/Concurrent Clinical Study Experience

25. Participated in another clinical trial of an investigational agent (or medical device) within 30 days or 5 half-lives of date of informed consent, whichever is longer, or is currently participating in another trial of an investigational agent (or medical device).

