4.1.3. Prior and Concomitant Medications

Prior and concomitant medications will be coded according to the March 2022 version of the World Health Organization (WHO) Drug Global dictionary (B3 format). Prior medications and non-medication therapies will be reported only in data listings.

Concomitant medications are defined as medications started prior to or after the start of study treatment and continued during the study or until the completion of the End of Study (EOS) visit. Prior medications are defined as those that both start and end before dosing.

Concomitant medications will be summarized descriptively for each stratum and overall by therapeutic subgroup (Anatomical Therapeutic Chemical [ATC] 2nd level), chemical subgroup (ATC 4th level) and preferred name for the FAS and displayed in data listings. Patients taking the same medication multiple times will be counted once per medication.

Concomitant procedures (non-medical therapies) will be coded using version 26.1 of the Medical Dictionary of Regulatory Activities (MedDRA). Concomitant procedures will be reported only in data listings.

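### SAP 3.9 moves a partial start date matching the month or year of first dose to Day 1 without checking a known earlier end date, so a record can start after it ended

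*SAP*

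**What the plan says.** SAP 3.9 (Missing Data) treats AE onset dates as follows.

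- Where only the day is unknown, the rule reads: "the onset day will be set to the first day of the month unless it is the same month and year as the first dose". For that matching month it adds: "the onset date will be assumed to be the date of treatment initiation".
- Where day and month are both unknown, it reads: "the day and month will be assumed to be January 1, unless the event occurred in the same year as the study treatment". For that matching year it adds: "the event onset will be coded to the date of first dose in order to conservatively report the event as treatment-emergent".
- Where nothing is known, onset is Day 1, with one exception: "unless the end date is prior to study start". If the exception applies, nothing is imputed and the event is not treatment-emergent.

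For medications the section adds: "Partial start dates for concomitant medications will be handled in the same manner as partial adverse event onset dates".

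SAP 4.1.3 then uses the dates to classify medications: "Prior medications are defined as those that both start and end before dosing". Concomitant medications are those that started before or after the start of treatment and continued during the study. Prior medications are only listed, while concomitant medications are tabulated on the Full Analysis Set.

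**The concern.** The stated aim of moving an uncertain onset to Day 1 is to err toward calling an event treatment-emergent. That makes sense when the timing really is uncertain. A record known to have ended before first dose is not uncertain, and the exception in the third branch shows that the authors saw this. As written, though, a record with no start information at all is handled correctly, while one with more information (a known year, or a known month and year) can be given a start later than its own end.

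At stake are the accuracy of the concomitant-medication table and, rarely, of the treatment-emergent AE tables, together with start-after-end records in the analysis data. The medication sentence also refers only to partial start dates, so it is unclear whether the exception reaches medications in any branch.

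**Working it through.** The plan states no figure to reproduce, so the check is to run the rule on test records. Inputs: the three branches of SAP 3.9, an assumed first dose on 15 June 2023, and study start in the exception read as first dose.

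| Start as recorded | Known end | Start under SAP 3.9 | Start with an end-date check |
|---|---|---|---|
| June 2023, day missing | 10 June 2023 | 15 June 2023 (after its end) | 1 June 2023 |
| 2023 only | 20 March 2023 | 15 June 2023 (after its end) | 1 January 2023 |
| March 2023, day missing | 10 June 2023 | 1 March 2023 | 1 March 2023 |
| 2022 only | 20 March 2023 | 1 January 2022 | 1 January 2022 |
| Completely missing | 20 March 2023 | not imputed | not imputed |
| June 2023, day missing | ongoing | 15 June 2023 | 15 June 2023 |

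Only the first two records go wrong, and only they change with the check. The end date plays no part in those two branches, so a year-only record that ended on 10 June would also be set to 15 June.

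**Medications.** Screening runs up to 42 days before W1D1 (Protocol Table 1-1, footnote a), so a drug stopped on 10 June 2023, 5 days before dosing, falls within it. Protocol 6.7.1 documents all medications taken from Screening onward as concomitant. With an imputed start on Day 1, the drug does not start before dosing and so fails the SAP 4.1.3 definition of prior. It does not clearly meet the concomitant definition either. Its class is undefined, or it is concomitant if the program treats everything not prior as concomitant.

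**Adverse events.** SAP 4.4.2 counts an event as treatment-emergent if it emerges or worsens from first dose, and an onset imputed to Day 1 meets that. Protocol 8.7.5 sends events between consent and first dose to medical history, except SAEs related to a protocol-mandated procedure. Only those SAEs can be affected.

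**How often a matching date would occur.** This is an illustration under assumptions that are not in the documents: true starts uniform over the 365 days before first dose, first-dose dates uniform over a 365-day year, and every record ended before dosing. There are 365 × 365 = 133,225 combinations.

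- Day missing: a first dose on day d of a month has d − 1 earlier days in that month. Summed over the year: 7 × 465 + 4 × 435 + 378 = 5,373, and 5,373 / 133,225 = 4.0%.
- Year only: a first dose on day k of the year has k − 1 earlier days in that year. The sum is 364 × 365 / 2 = 66,430, and 66,430 / 133,225 = 49.9%.

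These are shares of records that already have that kind of partial date. Courses started more than a year before dosing are never affected. Neither document says how many partial dates there are.

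**The case against.** The best defence is that the medication rule is confined to concomitant medications. A drug with a known end before dosing must also have started before dosing, so it is prior on its end date alone, whatever start is imputed. A sensible programmer might well work that way. But the SAP does not say that classification precedes imputation, its definition of prior depends on the start as well as the end, and Protocol 6.7.1 labels drugs taken in screening as concomitant. The defence narrows the harm without removing it.

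It is also fair to say that the consequences are slight. The medication table counts patients by ATC level and preferred name and shows no start dates, and recorded end dates remain visible in the listings. Procedure-related SAEs must be reported within 24 hours of knowledge, so a month-only or year-only onset is unlikely. All of this stands.

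A reader might infer something stronger: that washed-out anemia treatments would appear as on-study use and cast doubt on HI-E responses. The documents do not support that.

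- SAP 4.1.6 puts erythropoiesis-stimulating agents, G-CSF, luspatercept and lenalidomide in a data listing. Whether they also enter the 4.1.3 table is not stated.
- Protocol 5.2 criterion 20 excludes "Use of erythropoietin (ESA), other hematopoietic growth factor treatment or lenalidomide within 30 days of starting study treatment", with an exception for stable ESA use in chronic kidney disease. Criterion 21 sets 30 or 80 days for luspatercept. A course that ended at least 30 days before dosing can hardly have begun in the calendar month of first dose, so in practice only year-only starts could be affected.
- A course that ended before consent and before the 30-day medication look-back in Protocol 8.1.4 is not a screening medication at all.
- HI-E in SAP 4.2.1.1 is built from hemoglobin and RBC transfusions and uses no medication flag. Transfusion history dates have their own rule in SAP 3.9, and SAP 5.2 drops the Per-Protocol Set.

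Nor can a percentage of affected washout courses be given, because it would need course lengths and a rate of year-only dates that the documents do not supply.

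**Conclusion.** The rule is wrong as written, but the point is minor. In two of the three branches, a record known to have ended before first dose can be given a Day 1 start later than its own end. For medications, this can move a drug stopped during screening out of the prior class and possibly into the concomitant table. For AEs, it can make a screening-procedure SAE treatment-emergent, which should be rare. Only partial dates matching the month and year, or the year alone, of first dose are affected. The primary endpoint does not change.

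The test records rest on a literal reading of SAP 3.9 with imputation before classification. The 4.0% and 49.9% shares rest on the uniform-date assumptions and do not estimate how many records this trial has.

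**What to change.** Apply the end-date exception to all three branches and state it for medications. Suggested text for SAP 3.9:

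> If the known end date is before first dose, the start or onset is not imputed to first dose; the medication is classed as prior and the event as not treatment-emergent. An imputed start may not be later than the known end date.

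Partial starts caught by the check can keep the section's existing defaults, first of the month or January 1, which cannot fall after the known end. Naming first dose as the reference also avoids the looser term study start in the present exception. The cost is one SAP sentence and one programming condition, with no change to data collection or to the efficacy analyses.
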